### **8.11.6 Survival Follow-up Contacts**

Participants who experience confirmed disease progression or start a new anticancer therapy will move into the Survival Follow-up Phase and should be contacted every 12 weeks to assess for survival status until death, withdrawal of consent, or the end of the study, whichever occurs first.

The Sponsor may request survival status be assessed at additional time points during the course of the study. All participants who are not known to have died before the request for these additional survival status time points will be contacted at that time.

After approval of Protocol amendment 04, participants in the Survival Follow-up phase will be discontinued from the study and no further visits will be required.

#### **8.11.7 Vital Status**

To ensure current and complete survival information (vital status) is available at the time of database locks, updated vital status may be requested during the study by the Sponsor. Upon Sponsor notification, all participants who do not/will not have a scheduled study visit or study contact during the Sponsor-defined time period will be contacted for their vital status.

## 9 STATISTICAL ANALYSIS PLAN

This section outlines the statistical analysis strategies and procedures for the primary and secondary analyses of the study. Exploratory and other nonconfirmatory analyses will be outlined in a separate sSAP.

If, after the study has begun, changes are made to primary and/or secondary objectives, or the statistical methods related to those objectives, then the protocol will be amended (consistent with ICH Guideline E9). Changes to exploratory or other nonconfirmatory analyses made after the protocol has been finalized, but prior to the conduct of any analyses, will be documented in the sSAP as needed and referenced in the CSR for the study. Post hoc exploratory analyses will be clearly identified in the CSR.

### 9.1 Statistical Analysis Plan Summary

Key elements of the statistical analysis plan are summarized below; the comprehensive plan is provided in Sections 9.2 through 9.12.

Study Design Overview	This is an open-label, multicenter, dose escalation, phase I study of nemtabrutinib in Japanese participants with Mature B-cell neoplasms who have failed or are intolerant to previous treatment.
Intervention Assignment	A minimum of 3 participants up to a maximum 6 participants per dose level will be enrolled.
Analysis Populations	Safety: All-Participants-as-Treated (APaT) and Dose limiting toxicity-evaluable Efficacy: All-Participants-as-Treated (APaT) Pharmacokinetic: Per-Protocol (PP)
Primary Endpoint(s)	Dose-limiting toxicity (DLT) Adverse event (AE) Discontinuing study treatment due to an AE
Secondary Endpoints	PK parameters (AUC, Cmax, Tmax and Cmin) Objective response as assessed by investigator Duration of response as assessed by investigator
Statistical Methods for Key Efficacy Analyses	ORR will be estimated using an exact method based on the binomial distribution (Clopper-Pearson interval) together with its 95% confidence interval.
Statistical Methods for Key Safety Analyses	Summary statistics (counts, percentages, means, standard deviations, etc.) will be provided for the safety endpoints as appropriate. The pool-adjacent-violators-algorithm [Ji, Y., et al 2007] will be used to estimate the DLT rates across doses. The estimate of the DLT rate by dose level and the 90% Bayesian credible interval based on a prior distribution of Beta (1,1) for the estimate will be provided.
Statistical Methods for Key Pharmacokinetic Analyses	The plasma concentrations of nemtabrutinib will be summarized by planned visit and time for each dose separately. PK parameters will be summarized by dose.

Interim Analyses	No interim analysis is planned. Data will be examined on a continuous basis to allow for dose finding decisions.
Multiplicity	There will be no multiplicity control in this study since no hypothesis testing is planned.
Sample Size and Power	Each dose level assessed will have a minimum of 3 participants. Based on the occurrence of DLTs, up to 6 participants may enroll per dose level. The actual sample size is dependent on the number of dose levels tested and emerging safety data.

## 9.2 Responsibility for Analyses/In-house Blinding

The statistical analyses of the data obtained from this study will be the responsibility of the Clinical Biostatistics department of the Sponsor.

This study is being conducted as an open-label study, i.e., participants, investigators, and sponsor personnel will be aware of participant intervention assignment after each participant is enrolled and treatment is assigned.

## 9.3 Hypotheses/Estimation

Objectives and hypotheses of the study are outlined in Section 3.

## 9.4 Analysis Endpoints

### 9.4.1 Safety Endpoints

The primary safety endpoints are the number/proportion of participants with DLTs, with AEs, and who discontinue study treatment due to AEs. In addition, safety and tolerability will be assessed by clinical review of all relevant parameters including AEs, laboratory tests, and vital signs.

A description of safety measures is provided in Section 8.3 and Section 8.4.

### 9.4.2 Efficacy Endpoints

- Objective Response (OR)

OR is defined as participants who achieve at least a PR, per disease-specific criteria (see Section 8.2.1) as assessed by investigator. Objective response rate (ORR) is the proportion of participants in the analysis population with objective response.

- Duration of Response (DOR)

For participants who demonstrate an objective response as assessed by investigator, per disease-specific criteria, duration of response is defined as the time from the first documented evidence of an objective response until disease progression or death due to any cause, whichever occurs first.

### **9.4.3 Pharmacokinetic Endpoints**

Pharmacokinetic endpoints include plasma concentrations of nemtabrutinib, as well as any derived PK parameters. PK parameters include nemtabrutinib AUC, Cmax, Tmax and Cmin after the first dose (at Cycle 1 Day 1) and at steady-state.

## **9.5 Analysis Populations**

### **9.5.1 Safety Analysis Populations**

Safety Analyses will be conducted in the APaT population, which consists of all allocated participants who received at least one dose of study treatment.

The DLT evaluable population includes APaT participants that meet the criteria for DLT evaluability. See Section 4.3.1 and Section 5.5 for details.

At least one laboratory, vital sign, or ECG measurement obtained subsequent to at least one dose of study treatment is required for inclusion in the analysis of the respective safety parameter. To assess change from baseline, a baseline measurement is also required.

### **9.5.2 Efficacy Analysis Population**

Efficacy analyses will be conducted in the APaT population.

### **9.5.3 Pharmacokinetic Analysis Populations**

The Per-Protocol (PP) population will be used for analysis of PK data in this study. The PP population consists of the subset of subjects who complied with the protocol sufficiently to ensure that the data they generated will be likely to exhibit the effects of treatment, according to the underlying scientific model. Compliance covers such considerations as exposure to treatment, availability of measurements, and absence of major protocol violations. Major protocol violators will be identified prior to the database lock, by individuals responsible for data collection/compliance, and its analysis and interpretation. Any subjects or data values excluded from analysis will be identified, along with the reasons for exclusion, in the CSR.

## **9.6 Statistical Methods**

This section describes the statistical methods that address the primary and secondary objectives. Analysis by dose level will be performed by the initially assigned dose level. Methods related to exploratory endpoints will be described in the sSAP.

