## 4 STUDY DESIGN

### 4.1 Overall Design

This is a Phase 1, open-label, multisite, dose escalation study of nemtabrutinib in Japanese participants with Mature B-cell neoplasms who have failed or are intolerant to previous treatment. This study will evaluate the safety, tolerability, PK and preliminary efficacy of nemtabrutinib.

The study design is shown in [Figure 1](#). This study will enroll patients according to a modified toxicity probability interval (mTPI) design and perform dose escalation of nemtabrutinib at each predetermined dose levels (45 mg QD or 65 mg QD). To evaluate the DLT, participants will be enrolled to one dose level at the same time. Study medication will be administered at the following dose levels;

- Dose level 1 (DL1): 45 mg QD
- Dose level 2 (DL2): 65 mg QD

Details of DLT assessment schedules and rules are described in Section 4.3.2. The definition of DLTs is provided in Section 4.3.1. In principle, during DLT assessment period, participants will be hospitalized.

AEs will be evaluated by the investigator, according to criteria outlined in the NCI-CTCAE, version 5.0, to establish the safety and tolerability of nemtabrutinib monotherapy per the primary objective of this study.

Secondary objectives of this study are to evaluate PK following administration of nemtabrutinib and to evaluate ORR and DOR assessed by the investigator using assessment criteria of each disease as a preliminary efficacy evaluation. PFS and OS assessed by the investigator using assessment criteria of each disease are evaluated as tertiary/exploratory objectives.

Treatment response assessments may include computed tomography (CT)/magnetic resonance imaging (MRI) and/or positron emission tomography (PET) imaging, and laboratory assessments. Treatment response assessments will be performed during screening, every 12 weeks ( $\pm 7$  days), and every 24 weeks ( $\pm 7$  days) after 4 years and should follow calendar days from C1D1.

Patients will continue taking nemtabrutinib 45 mg or 65 mg QD until unacceptable toxicity, disease progression, or another discontinuation criterion described in Section 7.1 is met.

In or after cycle 4, participants receiving 45 mg of nemtabrutinib may be escalated to the 65 mg if the tolerability is confirmed at the 65 mg of nemtabrutinib and at the discretion of the investigator after discussion with the participant, upon the consultation with the sponsor.

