## 6.6 Dose Modification (Escalation/Titration/Other)

Nemtabrutinib – any treatment interruption more than 21 consecutive days needs to be discussed with the sponsor.

In or after cycle 4, participants receiving 45 mg of nemtabrutinib may be escalated to the higher dose if the tolerability is confirmed at the 65 mg of nemtabrutinib and at the discretion of the investigator after discussion with the participant, upon the consultation with sponsor.

If the escalation is permitted, the higher dose can be utilized from the Day 1 of next cycle based on the approved date.

The participants who receive the higher dose of nemtabrutinib should perform site visit / telephone contact after 14 ( $\pm 3$ ) days and 28 ( $\pm 3$ ) days from the first dose of the escalated dose to assess adverse event. Refer to Section 1.3 for the detailed schedule.

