### **8.4.1 Time Period and Frequency for Collecting AE, SAE, and Other Reportable Safety Event Information**

All AEs, SAEs, and other reportable safety events that occur after the participant provides documented informed consent, but before intervention allocation, must be reported by the investigator if the participant is receiving placebo run-in or other run-in treatment, if the event causes the participant to be excluded from the study, or is the result of a protocol-

specified intervention, including, but not limited to washout or discontinuation of usual therapy, diet, or a procedure.

- All AEs from the time of intervention allocation through 30 days after cessation of study intervention must be reported by the investigator.
- All AEs meeting serious criteria, from the time of intervention allocation through 90 days after cessation of study intervention or 30 days after cessation of study intervention if the participant initiates new anticancer therapy, whichever is earlier, must be reported by the investigator.
- All pregnancies and exposure during breastfeeding, from the time of intervention allocation through the time required to eliminate systemic exposure after cessation of study intervention as described in Sections 5.1 and 8.3.6.2, or 30 days after cessation of study intervention if the participant initiates new anticancer therapy must be reported by the investigator.
- Additionally, any SAE brought to the attention of an investigator at any time outside the time specified above must be reported immediately to the Sponsor if the event is considered related to study intervention.

Investigators are not obligated to actively seek AEs or SAEs or other reportable safety events in former study participants. However, if the investigator learns of any SAE, including a death, at any time after a participant has been discharged from the study, and the investigator considers the event to be reasonably related to the study intervention or study participation, the investigator must promptly notify the Sponsor.

All initial and follow-up AEs, SAEs, and other reportable safety events will be recorded and reported to the Sponsor or designee within the time frames as indicated in [Table 10](#).

Exception: A positive pregnancy test at the time of initial screening is not a reportable event unless the participant has received study intervention.

Table 10 Reporting Time Periods and Time Frames for Adverse Events and Other Reportable Safety Events

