### **9.6.1 Statistical Methods for Safety Analysis**

The broad AE categories consisting of the percentage of participants with any AE, a drug-related AE, a SAE, an AE which is both drug-related and serious, who discontinued due to an AE, and who discontinued due to a drug-related AE will be summarized by counts and frequencies for each dose level. Laboratory tests, vital signs, and other safety endpoints will be summarized as appropriate.

DLT will be listed and summarized by dose level. The pool adjacent violators-algorithm, which forces the DLT rate estimates to be nondecreasing with increasing dose levels and pools adjacent violators for weighted estimates by sample size, will be used to estimate the DLT rates across doses. The estimate of the DLT rate by dose level and the 90% Bayesian credible interval based on a prior distribution of Beta (1,1) for the estimate will be provided.

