### 9.6.3 Statistical Methods for Pharmacokinetic Analysis

Plasma concentrations of nemtabrutinib will be summarized by planned visit and time for each dose level separately. PK parameters will be summarized by dose level. Details of statistical analysis of pharmacokinetic analyses will be documented in the sSAP as appropriate.

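### Adverse events that start at 65 mg in participants escalated from 45 mg are tabulated under 45 mg, and no 65 mg safety summary includes them

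*Combined protocol and SAP*

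**What the plan says.** Section 9.6 states that "Analysis by dose level will be performed by the initially assigned dose level". Under that rule, Section 9.6.1 says that the AE categories (any, drug-related, serious, serious and drug-related, leading to discontinuation, and discontinuation for a drug-related AE) "will be summarized by counts and frequencies for each dose level". Section 9.4.1 makes these primary: "The primary safety endpoints are the number/proportion of participants with DLTs, with AEs, and who discontinue study treatment due to AEs".

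Dose is not fixed within a participant. Section 4.1: "In or after cycle 4, participants receiving 45 mg of nemtabrutinib may be escalated to the 65 mg if the tolerability is confirmed". Sections 6.6 and 8.11.2 repeat this, and treatment then runs until progression, unacceptable toxicity or another stopping criterion.

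Events after escalation are collected. Section 8.4.1: "All AEs from the time of intervention allocation through 30 days after cessation of study intervention must be reported by the investigator". Section 6.6 adds a visit or call 14 and 28 days "from the first dose of the escalated dose to assess adverse event".

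For objective response only, Section 9.6.2 adds a second analysis that pools everyone who at some point receives 65 mg. Section 9.12 reports exposure as days on treatment and does not split it by dose.

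**The concern.** Read together, Sections 9.6 and 9.6.1 place a 65 mg event in the 45 mg column whenever the participant started at 45 mg. Two things follow. The 45 mg column can show toxicity that did not arise at 45 mg. The 65 mg column describes only those who started at 65 mg, even when others have taken that dose for many cycles.

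At stake is what the study can report on two of its three primary endpoint components (AEs and discontinuation due to AEs) at the dose that Section 4.3 names as the RP2D. The plan is also uneven: the same 65 mg exposure can count towards response at 65 mg (Section 9.6.2) but not towards toxicity at 65 mg. The contacts at 14 and 28 days gather safety data specifically after escalation, and no planned by-dose summary credits those data to 65 mg.

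**Working it through.** **1. The plan's own figures.** Two dose levels of 3 to 6 participants give 2 × 3 = 6 to 2 × 6 = 12, as the synopsis states. Table 12 follows from the 5% and 95% quantiles of Beta(1 + x, 1 + n − x). For 0/3 these are 1 − 0.95^(1/4) = 0.013 and 1 − 0.05^(1/4) = 0.527; for 2/6 they are 0.129 and 0.659. All 11 intervals reproduce to three decimals. They concern DLTs.

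**2. What escalation can reach.** The earliest escalation is in Cycle 4.

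| Quantity | Window | Reached by escalation? |
|---|---|---|
| DLT, mTPI decisions | Cycle 1 (4.3.1) | No |
| Scheduled PK | Cycles 1 to 3 (4.2.1.3, Table 1) | No |
| AEs, SAEs | To 30 days after the last dose; SAEs to 90 days, or 30 if new anticancer therapy starts (8.4.1) | Yes; no supplementary summary |
| Discontinuation due to AE | Any time on treatment | Yes; no supplementary summary |
| Objective response | On treatment and efficacy follow-up | Yes; 9.6.2 adds a pooled 65 mg analysis |

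So the gap lies in the AE-based summaries.

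**3. How much exposure can be misplaced.** A participant escalated at the start of Cycle 4 and treated through Cycle 27 spends (27 − 3)/27 = 24/27 = 89% of cycles at 65 mg, all of it labelled 45 mg. Because Section 9.12 gives total days only, a reader cannot correct for this.

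**4. Size of one misplacement.** One participant is 1/6 = 17 percentage points of a column of 6, and 1/3 = 33 points of a column of 3. The 45 mg percentage for a category moves only if the participant had no event in that category before escalating. A discontinuation due to an AE after escalation always moves it. The omission from 65 mg occurs either way.

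**5. Illustration for the 45 mg column (assumed risks).** Let q be the risk of a given AE at 45 mg, p the risk after escalation, and f the fraction of 45 mg starters who escalate. With the two risks independent, the expected rate in the 45 mg column is 1 − (1 − q)(1 − fp).

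- q = 10%, p = 20%: f = 0 gives 10%; f = 0.5 gives 1 − 0.9 × 0.9 = 19%; f = 1 gives 1 − 0.9 × 0.8 = 28%.
- q = 10%, p = 30%: f = 0 gives 10%; f = 1 gives 1 − 0.9 × 0.7 = 37%.

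**6. Illustration for 65 mg (assumed risks).** The 65 mg safety denominator stays at the 3 to 6 who start there. If every 45 mg starter escalated, it could be 6 to 12. The chance of seeing at least one case of an AE with true incidence p is 1 − (1 − p)^n.

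| p | n = 6 | n = 12 |
|---|---|---|
| 5% | 26.5% | 46.0% |
| 10% | 46.9% | 71.8% |
| 20% | 73.8% | 93.1% |

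The n = 12 column is the ceiling. It takes six per level, all six escalating, and post-escalation risk equal to the risk of those who start at 65 mg.

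**The case against.** The best defence is that Section 4.1 defines the dose levels as cohorts, and that summarising by starting cohort is a clear, prespecified choice. It describes correctly what happens to people who start at 45 mg with the option to go up. No decision rests on the table: dose finding uses DLTs, the RP2D came from other studies, and no hypothesis test is planned. All of this stands. It supports keeping the initial-dose table, and it limits how serious the point is. It does not supply a description of AEs while participants take 65 mg.

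A reader might infer more than the documents support:

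- *That every by-dose analysis is affected.* Section 9.6.2 supplements objective response, and DLTs and scheduled PK are complete before Cycle 4.
- *That the PK summaries are biased.* Section 9.6.3 does say that "PK parameters will be summarized by dose level", and an early dose reduction could put a Cycle 2 or 3 sample under the wrong dose. But Section 9.5.3 counts exposure to treatment among the compliance considerations and provides for excluding individual data values, and Section 9.6.3 leaves PK detail to the sSAP.
- *That 65 mg safety data are discarded.* They are collected, kept in the APaT population and reviewed clinically. They sit in the wrong column for a question about dose taken.
- *That a misplaced AE discontinuation is likely.* Applying the 20.6% rate from BELLWAVE-001 gives 1 − 0.794³ = 50% for three escalated participants and 1 − 0.794⁶ = 75% for six. That rate covers all doses and all treatment from the first dose. The calculation also assumes that every 45 mg starter escalates, whereas escalation is optional and limited to people still on treatment at Cycle 4.

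**Conclusion.** The point holds for AEs, SAEs and discontinuations due to AEs. Events that start at 65 mg after escalation are reported under 45 mg, and nothing in the protocol or Section 9 provides a 65 mg safety summary that includes them. The sSAP is not available. Section 9 assigns it exploratory and other nonconfirmatory analyses, so a summary of primary safety endpoints belongs in Section 9.6.1.

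The size cannot be fixed from the documents. It ranges from nothing, if no one escalates, to all six participants of a full 45 mg cohort. Each misplaced participant is worth 17 to 33 percentage points of a column of 6 or 3. The rates in the illustrations are assumptions. This should be fixed because it limits what the study can say about safety at the RP2D. It does not undermine dose finding or the DLT estimates.

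**What to change.** Keep the initial-dose AE table. Add to Section 9.6.1 a supplementary summary by the dose being taken:

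- Assign AEs and SAEs by dose at onset, and discontinuations by dose at the time of discontinuation. The separate rule is needed because an AE that begins at 45 mg may lead to stopping at 65 mg.
- Show post-escalation 65 mg events in their own 45-to-65 mg column, and again in an all-65 mg total counted from each participant's first 65 mg dose.
- Give exposure time at each dose beside the counts.
- State in a footnote that escalated participants are selected for having tolerated 45 mg, so the all-65 mg total may understate risk in people who start at 65 mg.
- Apply the same dose-at-the-time rule after the dose reductions in Table 5.

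No new data are needed, since Section 6.6.1 already requires dose changes to be captured in the EDC system. The cost is one extra table set and an edit to Section 9. That edit goes by protocol amendment, because Section 9 requires one when methods tied to primary objectives change.

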### **9.6.1 Statistical Methods for Safety Analysis**

The broad AE categories consisting of the percentage of participants with any AE, a drug-related AE, a SAE, an AE which is both drug-related and serious, who discontinued due to an AE, and who discontinued due to a drug-related AE will be summarized by counts and frequencies for each dose level. Laboratory tests, vital signs, and other safety endpoints will be summarized as appropriate.

DLT will be listed and summarized by dose level. The pool adjacent violators-algorithm, which forces the DLT rate estimates to be nondecreasing with increasing dose levels and pools adjacent violators for weighted estimates by sample size, will be used to estimate the DLT rates across doses. The estimate of the DLT rate by dose level and the 90% Bayesian credible interval based on a prior distribution of Beta (1,1) for the estimate will be provided.

